4.5. Exploratory Endpoints Analysis

Table GPHM.4.4. Exploratory Efficacy Analysis

Objective	Relative to the Efficacy Measure	Analysis Conducted
Compare tirzepatide MTD QW with placebo for body weight reduction at 72 weeks	Percentage of participants achieving $\geq 25\%$ body weight reduction from randomization at 72 weeks	Logistic model in Section 4.3.2.2
Compare tirzepatide MTD QW with placebo for body weight reduction at 72 weeks	Percentage of participants achieving $\geq 10\%$, 15%, 20%, and 25% body weight reduction from Week -12 at 72 weeks	Logistic model in Section 4.3.2.2
Assess changes in BMI from Week -12 at Week 0	Percentage of participants whose BMI shifts between clinically relevant categories, that is, from Week -12 (<25, 25 to <30, 30 to <35, 35 to <40, ≥ 40) to Week 0 (<25, 25 to <30, 30 to <35, 35 to <40, ≥ 40)	Shift analysis will be conducted based on data from enrolled participants.
Compare tirzepatide MTD QW with placebo for BMI shifts from Week 0 at 72 weeks	Percentage of participants whose BMI shifts between clinically relevant categories, that is, from Week 0 (<25, 25 to <30, 30 to <35, 35 to <40, ≥ 40) to 72 weeks (<25, 25 to <30, 30 to <35, 35 to <40, ≥ 40)	Shift analysis will be conducted based on data from the EAS.
Visualize tirzepatide MTD QW and placebo percentage of body weight reduction, from Week -12 up to the safety follow-up after 72 weeks	Percentage of body weight reduction from Week -12 to 72 weeks plus 4 weeks safety follow-up	Time-course plot will be generated. Only the participants who complete the 72 weeks of treatment and have the safety follow-up visit (Visit 801) will be included.
Assess changes from Week -12 at Week 0 and compare tirzepatide MTD QW with placebo in parameters from Week -12 at 72 weeks	Mean change in 
 • systolic blood pressure • diastolic blood pressure • total cholesterol • HDL-C • non-HDL-C • LDL-C • VLDL-C • triglycerides • free fatty acids • fasting glucose • HbA1c • fasting insulin 	For analysis from Week -12 at Week 0, change from baseline to postbaseline values at each scheduled visit will be summarized. Within-treatment difference will be assessed by a Wilcoxon signed-rank test. For analysis from Week -12 at 72 weeks, the MMRM model in Section 4.3.2.2 for parameters with repeated measurements will be used. An ANCOVA model for parameters with only 1 postbaseline measurement will be used.
Assess changes in lipid parameters from Week -12 at Week 0	Percentage of participants whose Lipid parameters shift between clinically relevant categories: 
 • LDL-C (<70, 70 to <160, 160 to <190, ≥ 190 mg/dL) • HDL-C (male: <40, ≥ 40mg/dL, female: <50, ≥ 50mg/dL) 	Shift analysis will be conducted based on data from enrolled participants.

	
 Triglycerides (<150, 150 to <170, 170 to <500, ≥500mg/dL) 	
Compare tirzepatide MTD QW with placebo for changes in lipid parameters from Week 0 at 72 weeks	
Percentage of participants whose Lipid parameters shift between clinically relevant categories:
 
 LDL-C (<70 mg/dL, 70 to <160 mg/dL, 160 to <190 mg/dL, ≥190 mg/dL) HDL-C (male: <40 mg/dL, ≥40mg/dL, female: <50 mg/dL, ≥50mg/dL) Triglycerides (<150 mg/dL, 150 to <170 mg/dL, 170 to <500 mg/dL, ≥500mg/dL) 	Shift analysis will be conducted based on data from the EAS.
Assess change in fasting glucose category from Week -12 at Week 0	Percentage of participant change in fasting glucose category, that is, from Week -12 (<100 mg/dL, 100-125 mg/dL, ≥126 mg/dL) to Week 0 (<100 mg/dL, 100-125 mg/dL, ≥126 mg/dL)	Shift analysis will be conducted based on data from enrolled participants.
Compare tirzepatide MTD QW with placebo for change in fasting glucose category from Week 0 at 72 weeks	Percentage of participant change in fasting glucose category, that is, from Week 0 (<100 mg/dL, 100-125 mg/dL, ≥126 mg/dL) to 72 weeks (<100 mg/dL, 100-125 mg/dL, ≥126 mg/dL)	Shift analysis will be conducted based on data from the EAS.
Assess change in HbA1c category from Week -12 at Week 0	Percentage of participant change HbA1c category, that is, from Week -12 (<5.7%, 5.7% to 6.4%, ≥6.5%) to Week 0 (<5.7%, 5.7% to 6.4%, ≥6.5%)	Shift analysis will be conducted based on data from enrolled participants.
Compare tirzepatide MTD QW with placebo for change in HbA1c category from Week 0 at 72 weeks	Percentage of participant change HbA1c category, that is, from Week 0 (<5.7%, 5.7% to 6.4%, ≥6.5%) to 72 weeks (<5.7%, 5.7% to 6.4%, ≥6.5%)	Shift analysis will be conducted based on data from the EAS
Assess change for patient-reported outcome measurements change from Week -12 to Week 0	Mean change in patient-reported outcome measurements (Section 4.7.1)	Data from Week -12 to Week 0 will be included. Change from baseline to postbaseline values at each scheduled visit will be summarized. Within-treatment difference will be assessed by a Wilcoxon signed-rank test.
Compare tirzepatide MTD QW with placebo for patient-reported outcome measurements change from Week 0 to 72 weeks	Mean change in patient-reported outcome measurements (Section 4.7.1)	Data from Week 0 to 72 weeks will be included. An ANCOVA model with terms of treatment (tirzepatide MTD, placebo), country/pooled country, sex, and corresponding baseline score as a covariate will be used. Missing data will be imputed using LOCF.
Compare tirzepatide MTD QW with placebo for patient-reported outcome measurements change	Mean change in patient-reported outcome measurements (Section 4.7.1)	Data from Week -12 to 72 weeks will be included. An ANCOVA model with terms of treatment (tirzepatide MTD, placebo),

from Week -12 to 72 weeks		country/pooled country, sex, and corresponding baseline score as a covariate will be used. Missing data will be imputed using LOCF.
---------------------------	--	---

Abbreviations: ANCOVA = analysis of covariance; BMI = body mass index; EAS = Efficacy Analysis Set; HbA1c = hemoglobin A1c; HDL-C = high-density lipoprotein cholesterol; LDL-C = low-density lipoprotein cholesterol; LOCF = last observation carried forward; MMRM = mixed model for repeated measures; MTD = maximum tolerated dose; QW = once-weekly; VLDL = very low-density lipoprotein cholesterol.

In addition, the following endpoint analyses to assess the risk difference in proportions for an unconditional treatment effect (Ge et al. 2011) between tirzepatide MTD and placebo arm may be conducted:

- percentage of participants achieving at least 5% body weight reduction from randomization at 72 weeks
- percentage of participants achieving at least 10% body weight reduction from randomization at 72 weeks
- percentage of participants achieving at least 15% body weight reduction from randomization at 72 weeks
- percentage of participants achieving at least 20% body weight reduction from randomization at 72 weeks
- percentage of participants achieving at least 25% body weight reduction from randomization at 72 weeks

4.6. Safety Analyses

Unless specified otherwise, safety assessments for the double-blind period will be based on the SS (Table GPHM.3.1). All data collected between randomization and the end date of study participation will be included, regardless of the adherence to study drug.

Safety outcomes during the intensity lifestyle modification lead-in period will also be summarized for all enrolled participants. Detailed analyses can be found in Appendix 4 (Section 6.4).

The statistical assessment of homogeneity of the distribution of categorical safety responses between tirzepatide and placebo will be conducted using Fisher's exact test, unless specified otherwise.

The mean change from baseline differences among treatments at all scheduled visits will be assessed via an MMRM using REML. Unless specified otherwise, if the safety parameter is assessed at 72 weeks, then the model will include country/pooled country, sex, percentage of body weight reduction at the end of lead-in ($<10\%$ and $\geq 10\%$), treatment group, visit, and treatment-by-visit interaction as fixed effects and baseline value of the safety parameter as a covariate. To model the covariance structure within participants, the unstructured covariance matrix will be used. If this model fails to converge, the covariance structures specified in Section 4.3.2.2 will be tested in order until convergence is met. If the data do not warrant the MMRM model, then an ANCOVA model will be conducted.

For selected parameters, time-to-first-event analysis via the Cox proportional hazards model may be conducted. Participants without the event will be censored at the end of study participation.

For participants experiencing the event, the “time-to-first-event” will be the time (in weeks) from first dose to first occurrence of the event.

Where necessary, the rate of events will be analyzed using a generalized linear mixed model, assuming the number of events follows a negative binomial distribution, with treatment as a fixed effect. The logarithm of days during the active treatment period will be adjusted as an offset, to account for possible unequal treatment duration of follow-up between participants.

Unless otherwise specified, all the analyses listed in this section will be conducted using up to 72 weeks treatment period, plus the safety follow-up (Visit 801), for all randomized participants.

4.6.1. Extent of Exposure

The summary of duration of follow-up (defined as time in days from the date of randomization to the date of the last study visit) and/or duration on study treatment (defined as time in days from the date of first dose of study treatment to the date of last dose of study treatment plus 7 days) will be provided by treatment group using data from the SS over 72 weeks, plus safety follow-up (Visit 801), for all randomized participants.

For the summary of duration on study and study treatment, the frequency and percentage of participants falling into the following ranges will be summarized by planned treatment group as well:

- >0
- ≥4 weeks
- ≥8 weeks
- ≥12 weeks
- ≥16 weeks
- ≥20 weeks
- ≥24 weeks
- ≥36 weeks
- ≥48 weeks
- ≥52 weeks, and
- ≥72 weeks.

In addition, the frequency and percentages of participants falling into the following study and study treatment exposure ranges may be summarized by planned treatment group:

- 0 weeks
- >0 to <4 weeks
- ≥4 to <8 weeks
- ≥8 to <16 weeks
- ≥16 to <24 weeks
- ≥24 to <36 weeks
- ≥36 to <48 weeks
- ≥48 to <52 weeks
- ≥52 to <72 weeks, and
- ≥72 weeks.

No p-values will be reported in these summaries, as they are intended to describe the study populations rather than test hypotheses about them.

4.6.2. Adverse Events

4.6.2.1. Treatment-Emergent Adverse Events

A treatment-emergent adverse event (TEAE) is defined as an event that first occurred, or worsened in severity, after baseline (defined in [Table GPHM.4.1](#)). The Medical Dictionary for Regulatory Activities (MedDRA) Lowest-Level Term (LLT) will be used in the treatment-emergent derivation. The maximum severity for each LLT during the baseline period, including ongoing medical history, will be used as baseline severity. Events with a missing severity during the baseline period will be treated as “mild” in severity for determining treatment-emergence. Events with a missing severity during the postbaseline period will be treated as “severe”, and treatment-emergence will be determined by comparing to baseline severity.

For events occurring on the day of first taking study medication, the information collected in the case report form (CRF) (for example, treatment-emergent flag, start time of study treatment and event) will be used to determine whether the event was pre- or posttreatment. If the relevant information is not available, then the events will be counted as posttreatment.

In an overview table, the counts and percentages of participants who experienced a TEAE, serious adverse event (SAE), death, or discontinued from study and/or study treatment due to an adverse event (AE) will be summarized by treatment.

The counts and percentages of participants with TEAEs will be summarized by treatment using MedDRA Preferred Terms (PTs) nested within System Organ Class (SOC). Events will be ordered by decreasing frequency within SOC. System Organ Classes will be presented in alphabetical order. Statistical comparisons will be applied at both the SOC and PT levels. If necessary, the percentages of participants with TEAEs will also be summarized by treatment using MedDRA PT (without regard to SOC) by decreasing frequency.

The counts and percentages of participants with TEAEs will be summarized by maximum severity and treatment using MedDRA PTs. For each participant and TEAE, the maximum severity for the MedDRA PT is the maximum postbaseline severity observed from all associated LLTs mapping to the MedDRA PT. Maximum severity will be determined based on the nonmissing severities. If all severities are missing for the defined postbaseline period of interest, it will show as missing in the table.

4.6.2.2. Common Adverse Events

The counts and percentages of participants with TEAEs, overall and common (common TEAEs occurred in $\geq 5\%$ of participants in any treatment group before rounding), will be summarized by treatment using MedDRA PT. Events will be ordered by decreasing frequency.

4.6.3. Additional Safety Assessments

4.6.3.1. Deaths

A listing of all deaths during the study will be provided. The listing will include participant identification including the treatment, site number, participant number, date of death, age at the time of enrollment, sex, cause of death as reported by investigator, cause of death as adjudicated by the Clinical Evaluation Committee (CEC), and so on.

4.6.3.2. Other Serious Adverse Events

The counts and percentages of participants who experienced at least 1 SAE (including deaths and SAEs temporally associated with or preceding deaths) during the postbaseline period will be summarized by treatment using MedDRA PT nested within SOC. Events will be ordered by decreasing frequency within SOC. The SOCs will be in alphabetical order.

A listing of all SAEs will be provided. The listing will include treatment, participant identification including the site number, participant number, date of event, age at the time of enrollment, sex, MedDRA SOC and PT, reported term, severity, outcome, relationship to study drug, time from first dose of study drug to the event, AE start date, AE end date, severity, and action taken related to study treatment.

4.6.3.3. Other Significant Adverse Events

The counts and percentages of participants who discontinued from study treatment or study due to an AE during the postbaseline period may be summarized by treatment group using MedDRA PT nested within SOC. Events will be ordered by decreasing frequency within SOC.

4.6.3.4. Vital Signs

In the case that multiple measurements of an individual vital sign (for example, sitting SBP) are collected at the same visit, the mean of these measurements will be used for the analysis.

Vital signs (SBP, DBP, and pulse) will be summarized by treatment group at each planned visit. Change from baseline to postbaseline values for vital signs will be summarized for participants who have both a baseline and at least 1 postbaseline result. Treatment differences in mean change from baseline for vital signs will be assessed using the analysis model described in Section 4.6. Only planned measurements will be included in the mean change analyses.

The counts and percentages of participants with treatment-emergent abnormal (high or low) vital signs (sitting SBP, DBP, and pulse) at any time during the entire study (including the off-drug follow-up time period) will be summarized by treatment for participants who have both baseline and at least 1 postbaseline result. A treatment-emergent high result is defined as a change from a value less than or equal to the high limit at baseline to a value greater than the high limit at any time that meets the specified change criteria during the postbaseline period. A treatment-emergent low result is defined as a change from a value greater than or equal to the low limit at baseline to a value less than the low limit at any time that meets the specified change criteria during the postbaseline period. Both planned and unplanned measurements will be included in the analysis. The criteria for identifying participants with treatment-emergent vital signs abnormalities are listed in [Table GPHM.4.5](#).

Table GPHM.4.5. Categorical Criteria for Abnormal Treatment-Emergent Blood Pressure and Pulse Measurements

Parameter	Low	High
Systolic BP (mm Hg) (Supine or sitting - forearm at heart level)	≤ 90 and decrease from baseline ≥ 20	≥ 140 and increase from baseline ≥ 20 ≥ 129 and increase from baseline ≥ 20
Diastolic BP (mm Hg) (Supine or sitting - forearm at heart level)	≤ 50 and decrease from baseline ≥ 10	≥ 90 and increase from baseline ≥ 10
Pulse (bpm) (Supine or sitting)	< 50 and decrease from baseline ≥ 15	> 100 and increase from baseline ≥ 15

Abbreviation: BP = blood pressure.

In addition, the following analyses will be conducted by treatment:

- counts and percentages of participants who had resting pulse increases from baseline at 2 or more consecutive visits of more than 10 bpm and/or 20 bpm
- counts and percentages of participants who had resting pulse increases from maximum baseline ≥ 20 bpm at any postbaseline visit
- counts and percentages of participants who had at least 1 resting pulse at any postbaseline visit exceeding 100 bpm, and
- counts and percentages of participants who had at least 1 resting pulse exceeding 100 bpm occurring at 2 or more consecutive study visits.

4.6.3.5. Electrocardiograms

Summary statistics by treatment and by nominal visit will be provided for electrocardiogram (ECG) parameters (heart rate, PR, QRS, QT, and QT corrected using Fridericia's correction factor [QTcF] [$QTcF = QT / RR^{0.333}$]). When the QRS is prolonged (for example, a complete bundle branch block), QT and QTc should not be used to assess ventricular repolarization. Thus, for a particular ECG, the following will be set to missing (for analysis purposes) when QRS is ≥ 120 msec: QT and QTcF.

Change from baseline to postbaseline values for ECG parameters will be summarized for participants who have both a baseline and at least 1 postbaseline result. Treatment differences in mean change from baseline for heart rate and PR interval will be assessed using the analysis model described in Section 4.6. Only planned measurements will be included in the mean change analyses.

The counts and percentages of participants who meet following criteria at any time during the entire study period (including the safety follow-up time period) will be summarized by treatment group:

- treatment-emergent ECG abnormalities as listed in [Table GPHM.4.6](#).
- QT greater than 500 msec

- QTcF greater than 480 msec
- QTcF greater than 500 msec, and
- treatment-emergent increase from the maximum baseline in QTcF interval of greater than 30 msec, 60 msec, or 75 msec. Maximum baseline (see [Table GPHM.4.1](#) for details) will be the maximum nonmissing observation in the baseline period. The maximum value during the treatment period will be analyzed. Scheduled and unscheduled measurements will be included.

Table GPHM.4.6. Selected Categorical Limits for ECG Data

Parameter	Low		High	
	Males	Females	Males	Females
Heart rate (bpm)	<50 and decrease ≥15	<50 and decrease ≥15	>100 and increase ≥15	>100 and increase ≥15
PR interval (msec)	<120	<120	≥220	≥220
QRS interval (msec)	<60	<60	≥120	≥120
QTcF (msec)	<330	<340	>450	>470

Abbreviations: ECG = electrocardiogram; QTcF = Fridericia's corrected QT interval.

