##### **9.4.4.3. Special Safety Topics**

This section includes areas of interest whether due to observed safety findings, potential findings based on drug class, or agreed upon consultation with regulatory agencies for the reasons previously mentioned.

The following AEs are AEs of special interest (AESI) for this study:

- Severe hypoglycemia
- Major adverse cardiovascular events (adjudicated). Includes, but not limited to cardiovascular death, nonfatal myocardial infarction, nonfatal stroke, and hospitalization for heart failure
- Treatment-emergent supraventricular arrhythmias and cardiac conduction disorders
- Hepatobiliary disorders. Includes biliary colic, cholecystitis, and other gallbladder disease
- Severe GI events
- Acute renal events
- MDD/suicidal behavior and ideation
- Pancreatitis (adjudicated)
- C-cell hyperplasia and thyroid malignancies
- Allergic/hypersensitivity reactions. Includes injection site reactions and ADA formation

Summaries and analyses for the incidence of AESIs will be provided by treatment. The details of analysis of AESI will be provided in the SAP.

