4.1. General Considerations

Statistical analysis of this study will be the responsibility of Eli Lilly and Company (Lilly) or its designee. Some analyses and summaries described in this analysis plan may not be conducted if not warranted by data (for example, few events to justify conducting an analysis). Additional analyses of the data may be conducted as deemed appropriate.

Unless otherwise noted, all tests of treatment effects will be conducted at a 2-sided alpha level of 0.05, and the confidence interval (CI) will be calculated at 95%, 2-sided.

Unless specified otherwise, efficacy and safety will be assessed using the modified intent-to-treat (mITT) population, and data will be analyzed based on the assigned treatment (that is, not the actual treatment received by the participant). For submission to the US FDA to support the registration of tirzepatide for chronic weight management, the primary efficacy analysis will be conducted using the Full Analysis Set (FAS). For other purposes, the efficacy analysis of the double-blind period will be conducted using the Efficacy Analysis Set (EAS). Safety analysis of the double-blind period will be conducted using the Safety Analysis Set (SS).

Unless otherwise specified, for analyses in the double-blind period, baseline is defined as the last nonmissing data collected prior to or at randomization (prior to the first dosing of study drug). For analyses in the lead-in period, baseline is defined as the start of screening and ends prior to the intensive lifestyle modification program (typically at Week -12).

Summary statistics for continuous measures will include sample size, mean, standard deviation (SD), median, minimum, and maximum. The analysis model to make comparisons among treatment groups relative to continuous measurements assessed over time will be either analysis of covariance (ANCOVA) or an MMRM, with terms of treatment, visit, treatment-by-visit interaction, stratification factors, and corresponding baseline measurement as a covariate. An unstructured covariance structure will model the relationship of within-patient errors.

The Kaplan-Meier method will be used for estimation of cumulative event-free survival rates over time, and Cox proportional hazards regression analysis will be used to compare hazard rates among treatments.

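### SAP 4.6.3.5 summarises QTcF and QRS by arm but, without giving a reason, plans no adjusted between-arm difference with a confidence interval for either

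*SAP*

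**What the plan says.** SAP 4.6 gives a general rule for continuous safety measures: "The mean change from baseline differences among treatments at all scheduled visits will be assessed via an MMRM using REML". The model includes the stratification factors and the baseline value. Categorical safety outcomes default to Fisher's exact test. SAP 4.6.3.4 applies the model to all three vital signs (systolic and diastolic pressure, pulse).

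SAP 4.6.3.5 treats ECG data in three ways.

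- **Descriptive.** "Summary statistics by treatment and by nominal visit will be provided for electrocardiogram (ECG) parameters", and the list covers heart rate, PR, QRS, QT and QTcF. For change, "Change from baseline to postbaseline values for ECG parameters will be summarized for participants who have both a baseline" and at least one post-baseline result. Under SAP 4.1, "Summary statistics for continuous measures will include sample size, mean, standard deviation (SD), median, minimum, and maximum".
- **Model-based.** "Treatment differences in mean change from baseline for heart rate and PR interval will be assessed using the analysis model described in Section 4.6". QRS and QTcF are not named, and no reason is given.
- **Cut-off counts.** Table GPHM.4.6 sets high limits of 120 ms or more for QRS, and above 450 ms (men) or 470 ms (women) for QTcF. The text adds QTcF above 480 and 500 ms, and "treatment-emergent increase from the maximum baseline in QTcF interval of greater than 30 msec, 60 msec, or 75 msec". QT and QTcF are set to missing when QRS is 120 ms or more.

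Protocol 9.4.4.4.4 promises summaries of selected ECG parameters and Fisher's exact test on abnormal values. Protocol 9.4.4.3 lists "Treatment-emergent supraventricular arrhythmias and cardiac conduction disorders" among the adverse events of special interest.

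**The concern.** QTcF and QRS are continuous and, under the Schedule of Activities, are recorded before the first dose, at Weeks 24 and 72, at early discontinuation and at safety follow-up. A uniform shift of a few milliseconds carries few people across a distant limit. The cut-off tests can therefore be non-significant when a shift exists, and a report that leans on its formal tests could present that as reassurance.

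The two SAP sections also sit awkwardly together. Section 4.6 reads as though the model applies to every continuous safety measure, while Section 4.6.3.5 names two ECG parameters. A programmer cannot tell whether QTcF and QRS fall under the general rule. An adjusted comparison added after unblinding would carry less weight than one named in advance. At stake is the quality of the ECG safety report, not the efficacy conclusions.

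**Working it through.** **1. The plan's own power figures.** Protocol 9.2 and SAP 5 give 300 per arm, 25% dropout, a 12-point difference with SD 10, responder rates of 20% and 46%, and two-sided 0.05. So n = 300 × 0.75 = 225 per arm.

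- Means: Φ(12 / (10 × √(2/225)) − 1.96) = Φ(12.73 − 1.96), over 99.9%.
- Proportions: Φ((0.26 − 1.96 × 0.0443) / 0.0426) = Φ(4.06), or 99.998%.

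Both agree with the stated power above 90%. The documents state no ECG SD, margin or power, so every ECG input below is an assumption.

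**2. Comparison of mean change, 225 to 300 per arm.** Power = Φ(δ / (SD × √(2/n)) − 1.96); 95% CI half-width = 1.96 × SD × √(2/n). Assumed SD of QTcF change: 10 to 20 ms. For example, δ = 5, SD 15, n = 225 gives Φ(5 / 1.414 − 1.96) = Φ(1.58) = 94%. Half-widths run from 1.96 × 10 × √(2/300) = 1.6 ms to 1.96 × 20 × √(2/225) = 3.7 ms.

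**3. Cut-off tests by simulation.** Assumptions: normal values; QTcF mean 415 ms, total SD 18 ms; 35% men; reference for increases is the maximum of two pre-dose ECGs; outcome is the maximum of two or three post-baseline ECGs; Fisher's exact test at 0.05.

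| QTcF comparison | 5 ms shift | 10 ms shift |
|---|---|---|
| Increase above 30 ms | 0% (SD 10), 10–30% (SD 15), 25–46% (SD 20) | 1–12% (SD 10), 74–99% (SD 15–20) |
| Above 450/470 ms | 6–20% | 43–81% |
| Increase above 60 ms; above 480 ms | about 0% | about 0% |
| Difference in mean change | over 99.9% (SD 10), 94–98% (SD 15), 76–87% (SD 20) | over 99.9% |

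At SD 15, three post-baseline ECGs and 225 per arm, a 5 ms shift raises the proportion with an increase above 30 ms only from 1.1% to 3.2%, giving 19% power.

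**4. QRS.** Assumed mean 92 ms, total SD 10 ms. With SD of change 5 or 8 ms, the 120 ms limit has 1–5% power for a 3 ms shift and 12–31% for 5 ms. A mean comparison over SD 5 to 10 has 89% to over 99.9% for 3 ms.

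**5. Gain over the planned tables.** The descriptive tables give n, mean and SD of change by arm, so an unadjusted difference and CI follow directly. Take a between-person SD of 15 ms and an occasion SD of 9 or 12 ms. The SD of change is √2 × 9 = 12.7 or √2 × 12 = 17.0. Adjusting for baseline leaves √(T × (1 − ρ²)), where T is the total variance and ρ = 225/T:

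- T = 225 + 81 = 306, ρ = 0.735, residual SD 11.9.
- T = 225 + 144 = 369, ρ = 0.610, residual SD 15.2.

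| 225 per arm | Unadjusted | Baseline-adjusted |
|---|---|---|
| CI half-width, occasion SD 9 / 12 | 2.4 / 3.1 ms | 2.2 / 2.8 ms |
| Power, 5 ms | 98.6% / 87.8% | 99.4% / 93.6% |
| Power, 3 ms | 70.5% / 46.6% | 76.5% / 55.2% |

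The gain is 0.8 to 8.6 points.

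**The case against.** The other side has a strong case. SAP 4.6.3.5 meets what Protocol 9.4.4.4.4 promises and adds models for two parameters. Choosing which measures to model is SAP practice: SAP 4.6.3.6 does so for selected laboratory tests. Protocol 8.2.3 calls for single tracings with optional over-reading, so nothing suggests the trial was meant to exclude QTcF shifts of a few milliseconds. SAP 4.1 allows further analyses. Conduction disorders are of special interest as adverse events found by MedDRA search, not as mean QRS. All of this stands, and it keeps the severity low.

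Three stronger readings are tempting, and the documents do not support them.

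- A reader might infer that the arms are compared on QTcF and QRS only through cut-offs. The planned by-arm, by-visit summaries of values and change say otherwise, and a uniform 5 ms shift would be expected to show in those means.
- A reader might infer that the trial has almost no power for such shifts. Low power belongs to the cut-off tests, not to the data. For a 10 ms QTcF shift some cut-offs do well.
- A reader might infer a gain of 50 points or more. Gaps of that size appear only against the cut-off tests, and only under some of the assumed SDs.

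What the objection does not supply is a reason for leaving the two parameters out of a model already specified. Nor does a difference worked out by a reader replace a prespecified estimate adjusted for baseline and stratification factors.

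**Conclusion.** The point holds as a low-severity gap, a cheap improvement. No adjusted between-arm estimate or CI is prespecified for QTcF or QRS, and the formal tests that remain are insensitive to small shifts. Over the grid in step 3, the best QTcF cut-off trails the mean comparison by at least about 40 points for a 5 ms shift at the same SD and arm size; the narrowest gap is 86.5% against 46% (SD 20, 300 per arm).

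Measured against the planned descriptive tables, the gain is modest: a prespecified, adjusted estimate, a QTcF interval about 7–10% narrower (11.9/12.7 and 15.2/17.0), and 1 to 9 points of power at 3–5 ms. The ECG figures rest on assumed means and SDs, normal values and a uniform shift. The finding that the plan names no such estimate rests on the text alone.

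**What to change.** In SAP 4.6.3.5, extend the model sentence to four parameters. Suggested wording: *Between-arm differences in mean change for heart rate, PR, QRS and QTcF will be estimated with the Section 4.6 model, and the Week 72 difference will be reported with its 95% CI.* Keep all categorical limits and the rule that sets QT and QTcF to missing when QRS is 120 ms or more. If the omission is deliberate, state the reason instead.

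The cost is one sentence and two more runs of an existing model on data already collected. Sample size, alpha and conduct do not change. The downside is two more unadjusted safety comparisons, which is consistent with SAP 2.1, where safety assessments carry no multiplicity adjustment.
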